8.2 SAMPLE SIZE AND STATISTICAL POWER

Our study is powered appropriately for determination of the primary objective which involves the assessment of 2 doses of 5-ALA, 10mg/kg and 20mg/kg, to determine the optimum ALA dose in terms of both sensitivity and specificity for residual tumor. We calculate the total sample size for 80% power at the 0.05 significance level, given that the sensitivity will decrease by 15% with decreasing ALA dose within patient group (i.e. newly diagnosed or recurrent). Therefore our null hypothesis is that the sensitivity of the 10mg/kg dose is less than or equal to 15% different from the 20 mg/kg dose and the

alternative hypothesis is that the sensitivity of the 10mg/kg dose is greater than 15% different from the 20 mg/kg dose. We also take into account having multiple biopsies per individual on study. The total sample size per group per dose is as follows:

The primary objective of this Phase II study is to estimate and compare the combined diagnostic accuracy of in-vivo qualitative assessment of fluorescent signal in detecting residual tumor when used by the neurosurgeon using 2 doses of 5-ALA: 10 mg/kg and 20 mg/kg. The in-vivo qualitative assessment by the neurosurgeon will be coded on an ordinal scale ranging from 0 (no signal) to 3 (highest signal), as was done in a similar study reported by Roberts et al (J Neurosurg 2010 Apr 9, epub ahead of print) using a dose of 20 mg/kg in newly diagnosed gliomas. As in Roberts et al, we assume a score of 1 or higher will be considered positive. In the study by Roberts et al (2010) the reported sensitivity and specificity were 0.75 and 0.71, respectively, using the histopathologic reading as gold standard. In this study, because having high sensitivity and specificity are both important in terms of avoiding false negatives (which would involve not removing residual tissue) and false positives (removing normal tissue), the Youden index, defined as Sensitivity + Specificity -1 will be used as an overall measure of diagnostic accuracy. This study is designed so that if the dose levels of 10 and 20 mg/kg have true Youden indices that differ by 0.10 or more, then the probability is 80% or higher that the observed Youden index will be higher for the group with the higher actual index, i.e., the probability of selecting the correct dose level based on observed Youden indices will be 80% or higher.

For each patient, samples will be removed from six sites (2 center of tumor, 2 edge of tumor, and 2 adjacent normal tissue). It is assumed that on average, three samples will be tumor positive based on pathology, and three will be tumor negative. Thus, on average, each subject will contribute 3 true positive samples (used in estimating sensitivity), and 3 true negatives (used in estimating specificity). If n subjects per stratum (new or recurrent) are studied at a given dose, and π and θ are the sensitivity and specificity, we assume that the estimated sensitivity and specificity obtained as the proportions of true positives and true negatives are approximately normally distributed with means π and θ and respective variances $\pi(1-\pi)(1+2\rho)/3n$, and $\theta(1-\theta)(1+2\rho)/3n$, where ρ is the within-subject correlation of binary responses obtained for tissues on the same subject. This formula can be derived for example assuming a beta-binomial model to model extra-binomial variability. Here the term $(1+2\rho)$ is the design effect where the coefficient of ρ is $m-1$, where m is the number of true positive or true negative samples per subject. Given specified values of sensitivity and specificity for the two doses reflecting a scenario where Youden indices differ between doses, the probability that the better dose has the higher observed Youden index can be determined, and the sample size n determined such that this probability is high.

Table 1 below presents required numbers of patients per group in order to have 80% probability of correctly identifying the optimal dose, when the Youden indices of the two doses differ by 0.10, using a range of plausible values for sensitivity and specificity, for intrasubject correlations of $\rho=0.1$ and 0.2. **Based on these results it can be seen that with sample sizes of 30 glioblastoma multiformes (GBMs) there is a 80% or higher**

chance of correctly identifying the optimal dose when Youden indices differ by 0.10 or more. Assuming sample size n=30 and intrasubject correlation $\rho=0.2$, the 95% confidence intervals for $\pi=0.75$, $\theta=0.70$, and youden index=0.45 are (0.64, 0.86), (0.59, 0.81), and (0.23, 0.67), respectively.

Table 1. Required sample size per group to correctly identify the optimal dose with probability of 80%, when Youden indices differ by 0.10 between doses, for various combinations of sensitivity and specificity and intrac-subject correlation, ρ .

Dose=20 mg/kg			Dose=10 mg/kg			Δ Youden (20 – 10)	Required # subjects per group	
Sens	Spec	Youden	Sens	Spec	Youden		$\rho=0.10$	$\rho=0.20$
0.75	0.70	0.45	0.60	0.75	0.35	0.1	23	27
0.75	0.70	0.45	0.65	0.70	0.35	0.1	24	28
0.70	0.70	0.40	0.60	0.70	0.30	0.1	24	28
0.70	0.70	0.40	0.55	0.75	0.30	0.1	24	28
0.65	0.70	0.35	0.55	0.70	0.25	0.1	25	30
0.65	0.70	0.35	0.50	0.75	0.25	0.1	25	29
0.75	0.70	0.45	0.70	0.85	0.55	-0.1	21	24
0.75	0.70	0.45	0.75	0.80	0.55	-0.1	21	25
0.70	0.70	0.40	0.70	0.80	0.50	-0.1	22	26
0.70	0.70	0.40	0.65	0.85	0.50	-0.1	22	26
0.65	0.75	0.40	0.60	0.90	0.50	-0.1	21	25
0.65	0.70	0.35	0.60	0.85	0.45	-0.1	22	26

However, based on imaging, it is difficult to distinguish Grade IV malignant gliomas (GBMs) from Grade III tumors, otherwise known as anaplastic astrocytomas (AAs) in newly diagnosed patients. Traditionally, AA's account for 10-15% of all malignant gliomas with a rate of 11.1% reported for the US in 2010 (41). Assuming that 15% of all patients with newly diagnosed malignant gliomas have AA rather than GBM, we will need to accrue 35 patients to accrue 30 patients with newly diagnosed GBM. In the case of patients with recurrent malignant gliomas, all patients presenting with histological evidence of glioma who carry a diagnosis of GBM from an earlier surgery are considered to have "recurrent GBM" by convention. Patients carrying a diagnosis of AA who have recurrent have degenerated to GBM approximately half the time. Accordingly, of 33 patients with recurrent malignant glioma, 29 would be expected to have recurrent GBM, while 5 would be expected to have recurrent tumor arising from AA. Of the 5 with AA, two or three would be expected to have progressed to GBM.

Thus, in order to accrue 30 patients with newly diagnosed GBM, we will need to accrue 35 patients with newly diagnosed malignant glioma. In order to accrue 30 patients with recurrent GBM, we will need to accrue 33 patients with recurrent malignant glioma.

There are no planned interim analyses for efficacy because this is not a therapeutic trial. Monitoring of safety and trial progress will be the responsibility of the Data and Safety Toxicity Committee.

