4.4.2 LIGHT SENSITIVITY PRECAUTIONS

Before ALA administration, patients will be given verbal and written instructions for protection from sunlight by the staff surgeon or his delegate (see Section 4.7.1). It should be noted that these patients are hospitalized following surgery, so that there is in practice a very small possibility of their being exposed to bright sunlight outdoors. Nursing staff in the recovery room and on the ward will be instructed regarding the need to avoid accidental exposure to bright light in the first 24 hours.

4.4.3 .PATIENT GROUPS AND NUMBERS AND ALA DOSE

This clinical trial has ALA dose at 2 levels (10 and 20 mg/kg) and ALA administration time at 1 time point (3h). Consenting patients scheduled for surgery will be assigned to primary or recurrent arm based on clinical presentation, are then randomly assigned to one of two groups (for dose assignment) within each of the two arms of the study. Sample sizes of the 4 patient groups with two ALA dose levels are listed in the table below:

Table 3: Study Design and Sample Size

	Administration Time	
	3 hours New D _x	3 hours Recurrent D _x
10 mg/kg	30	30
20 mg/kg	30	30

For both patients with new and recurrent disease, biopsies will be taken at up to six sites identified by the surgeon: in the tumor center, tumor edge, area surrounding the tumor (if safe), areas seen to fluoresce intraoperatively and an area with MR enhancement outside

the tumor region (if this can be accomplished safely). Prior to collecting these biopsies readings will be taken at the biopsied location with the PpIX point probe by the surgeon. For each of the 6 biopsies, they will be divided into 3 parts and distributed for further analysis as follows: one portion will be sent to the pathologist for assessment of tumor percentage, one portion will be evaluated by the Division of Biophysics at the University of Toronto for PpIX concentration and the other for assessment of fluorescence.

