5.2 DATA ANALYSIS

5.2.1 FLUORESCENCE INTENSITY LEVELS VS. HISTOPATHOLOGY

The data sets will be collated into the 4 study groups (2 ALA doses and 2 study arms-- i.e., newly diagnosed and recurrent diagnosis) for analysis purposes.

Histopathology of the 1st part of the biopsies, performed by a single experienced neuropathologist (**i.e., [name]**) will be used as the gold standard. The white-light, fluorescence images, and intra-operative PpIX concentration readings will be compared to assess the sensitivity and specificity for biopsy-confirmed visible tumor.

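### Section 8.2 claims 80% power at the 0.05 level for a 15% fall in sensitivity, but n=30 comes from a Youden selection rule with no type I error control; against a no-difference null it gives 41–51% (two-sided) or 54–63% (one-sided) for a 15-point fall

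*Combined protocol and SAP*

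**What the plan says.** Section 8.2 gives two justifications for one sample size.

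- **A significance test on sensitivity.** The first paragraph says "We calculate the total sample size for 80% power at the 0.05 significance level, given that the sensitivity will decrease by 15" per cent. The comparison is made "with decreasing ALA dose within patient group (i.e. newly diagnosed or recurrent"). The hypotheses follow: "our null hypothesis is that the sensitivity of the 10mg/kg dose is less than or equal to 15% different from the 20 mg/kg dose", with a difference above 15% as the alternative. The paragraph ends by announcing the sample size per group per dose.
- **A selection rule on the Youden index.** The next paragraph says that if the true Youden indices differ by 0.10 or more, "the probability of selecting the correct dose level based on observed Youden indices will be 80% or higher". The variance formula and Table 1 of Section 8.2 serve this rule only; the table title reads "Required sample size per group to correctly identify the optimal dose with probability of 80" per cent. The conclusion is that "with sample sizes of 30 glioblastoma multiformes (GBMs) there is a 80% or higher" chance of picking the better dose.

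The figure of 30 applies to each dose within each stratum. Section 4.4.3 (Patient groups and numbers and ALA dose) lists four cells of 30 in its Table 3, and Section 5.2.1 says "The data sets will be collated into the 4 study groups".

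**The concern.** The two criteria are not interchangeable. A probability of correct selection asks only which observed index is larger. It has no critical value and does not control the chance of declaring a difference when none exists. A test with 80% power at 0.05 must also clear a critical value, which normally needs far more patients. An n derived from the first cannot be assumed to satisfy the second.

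The hypotheses raise a second problem. The planned effect is a 15% fall, and the null covers every difference up to and including 15%. The design effect therefore sits on the boundary of the null, where a valid 0.05-level test rejects about 5% of the time.

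This is the plan's only formal hypothesis and power statement, and it concerns the primary objective. A reader who trusts it could take a non-significant sensitivity difference as the result of a well-powered test and conclude that the lower dose loses little.

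**Working it through.** **Inputs, all from Section 8.2.** n=30 per dose per stratum; 3 tumor-positive and 3 tumor-negative samples per patient; variance of an estimated proportion p(1−p)(1+2ρ)/(3n); ρ = 0.1 and 0.2. Table 1 contains three pairs with a 15-point sensitivity fall: 0.75 to 0.60, 0.70 to 0.55 and 0.65 to 0.50.

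**Assumptions, because the plan is silent.** The 15% is read as percentage points, to match Table 1. One- and two-sided tests are both shown.

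**Step 1: reproduce Table 1.** With no significance level, the selection rule gives

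n = 0.8416² × Σp(1−p) × (1+2ρ) / (3 × 0.10²),

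summing over the sensitivity and specificity of both doses. For the first row, Σ = 0.1875 + 0.21 + 0.24 + 0.1875 = 0.825, so n = 23.4 at ρ=0.1 and 27.3 at ρ=0.2; the table prints 23 and 27. All 24 entries agree within one patient (largest gap 0.81). The largest value is 29.6, printed as 30. At n=30 the probability of correct selection is 80.2–84.4%. The selection claim is sound, and this rule is what produced n=30.

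**Step 2: power of the sensitivity test, null of no difference.**

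SE = √{[p₁(1−p₁) + p₂(1−p₂)](1+2ρ)/(3×30)}; power = Φ(0.15/SE − z), with z = 1.96 two-sided or 1.645 one-sided.

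For 0.75 to 0.60 at ρ=0.1: SE = √(0.4275 × 1.2/90) = 0.0755 and 0.15/SE = 1.99, so power is 51.1% two-sided and 63.4% one-sided.

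| Sensitivity, 20 to 10 mg/kg | SE (ρ=0.1 / 0.2) | Two-sided | One-sided | n per cell for 80%, two-sided | n per cell for 80%, one-sided |
|---|---|---|---|---|---|
| 0.75 to 0.60 | 0.0755 / 0.0815 | 51.1% / 45.2% | 63.4% / 57.7% | 60 / 70 | 47 / 55 |
| 0.70 to 0.55 | 0.0781 / 0.0844 | 48.4% / 42.8% | 60.9% / 55.3% | 64 / 75 | 51 / 59 |
| 0.65 to 0.50 | 0.0798 / 0.0862 | 46.8% / 41.3% | 59.3% / 53.8% | 67 / 78 | 53 / 62 |

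**Step 3: other readings.**

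- A pooled variance under the null changes power by about one point (40–50% and 53–63%).
- With no clustering (ρ=0), power is at most 59% two-sided and 70% one-sided.
- If 15% is relative (0.75, 0.70 or 0.65 multiplied by 0.85), power is about 21–33% two-sided and 30–45% one-sided.

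**Step 4: the hypotheses as written.** In a one-directional test against a 15-point margin, power at a true fall of exactly 15 points is 5%. For 80% power the true fall d must satisfy (d − 0.15)/SE = 1.645 + 0.842, which gives d of about 0.34–0.36.

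**The case against.** The best reply is that the Youden paragraph is the real design. It is stated explicitly, worked through and correct, and Section 8.1 contains no test of a 15% sensitivity margin. On that view the opening sentences were left beside the true calculation, nothing in the table is miscalculated, and neither the sample size nor the decision rule is wrong. All of this stands as a description of the harm: the fault is a false power claim and a mis-specified hypothesis pair, not a wrong n for the selection rule. It does not rescue the claim, which is still offered as the basis for saying the primary objective is adequately powered.

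It is also fair to say that 41–51% and 54–63% belong to a no-difference null that the plan does not write down. Under the null it does write, power at the planned effect is about 5%, so that choice favours the plan.

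A third reply is to combine the strata, giving 60 per dose. The same formula then gives 69–80% two-sided and 79–88% one-sided, so a one-sided combined test would largely reach the target. But Section 8.2 places the comparison within patient group and defines n per stratum, and combining assumes the same dose effect in new and recurrent disease.

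**Conclusion.** The concern holds. With 30 patients per dose per stratum, no reading of the within-group sensitivity claim reaches 80% power at 0.05: one- or two-sided, absolute or relative 15%, with or without clustering. In the main case, a true 15-point loss would be missed 49–59% of the time two-sided and 37–46% one-sided. The hypothesis pair fails independently of any variance assumption, because it puts the planned effect within the null.

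The figures rest on the plan's normal approximation, three positive samples for every patient, and ρ between 0.1 and 0.2. The probability of correct selection is unaffected and correct as stated.

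**What to change.** 1. Delete the sentence claiming 80% power at the 0.05 level and the null/alternative pair.
2. State what the sample size provides, for example: *Thirty evaluable GBM patients per dose per stratum give at least an 80% probability of selecting the dose with the higher true Youden index when the indices differ by 0.10, without control of type I error.*
3. State the within-stratum power for a 15-point sensitivity fall against no difference: 41–51% two-sided, 54–63% one-sided, for 20 mg/kg sensitivity 0.65–0.75, ρ 0.1–0.2 and three positive samples per patient.
4. Report the between-dose Youden difference with a 95% confidence interval. The expected half-width at ρ=0.2 is 1.96 × √[Σp(1−p) × 1.4/90] = 0.21–0.23 over the Table 1 rows. Section 8.2 prints (0.23, 0.67), a half-width of 0.22, for a *single* index of 0.45; the plan's formula gives about (0.30, 0.60). Correct that separate slip at the same time, or the difference will look about as precise as one index.
5. If a formal test is kept, write the null as no difference, state its sidedness, and say whether 15% is absolute or relative. A test stratified across new and recurrent disease is optional and should be labelled as assuming a common dose effect.

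The cost is rewording Section 8.2, with a less favourable power statement. Enrolment, randomization and the selection rule do not change. Keeping the plan's 80% power statement for a 15-point fall would instead need about 60–78 patients per cell two-sided (4 × 60 = 240 to 4 × 78 = 312 in all) or 47–62 one-sided (188 to 248), against the present 4 × 30 = 120.

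### Section 8.2 prints a 95% interval for the Youden index of (0.23, 0.67), which equals the sum of the separate sensitivity and specificity limits; the model behind Table 1 of that section gives (0.30, 0.60)

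*Combined protocol and SAP*

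**What the plan says.** Section 8.2 makes the Youden index (sensitivity plus specificity minus one) the overall accuracy measure. It sizes the trial so that, for true indices at least 0.10 apart, "the probability of selecting the correct dose level based on observed Youden indices will be 80% or higher".

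The section treats the estimated sensitivity and specificity as approximately normal. Each has variance p(1−p)(1+2ρ)/(3n), with three tumor-positive and three tumor-negative samples per patient on average. Here ρ "is the within-subject correlation of binary responses obtained for tissues on the same subject". No covariance between the two estimates is stated.

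Two results are then given:

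- Table 1 of section 8.2, titled "Required sample size per group to correctly identify the optimal dose with probability of 80%, when Youden indices differ by 0.10 between doses", lists 21 to 25 patients per group for ρ = 0.1 and 24 to 30 for ρ = 0.2.
- For n = 30 and ρ = 0.2, the 95% intervals for sensitivity 0.75, specificity 0.70 "and youden index=0.45 are (0.64, 0.86), (0.59, 0.81), and (0.23, 0.67), respectively".

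The section does not say how the Youden interval was built, and does not describe it as a conservative or simultaneous bound.

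**The concern.** The printed Youden limits are exactly what results from adding the sensitivity and specificity limits and subtracting one. The half-width of a sum of two estimates is not the sum of their half-widths unless the estimates move together perfectly. Table 1 depends on the variance of the same Youden estimate, so the interval and the table should rest on the same covariance assumption.

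This is the only precision figure the plan offers for the Youden index. Anyone who works back from the printed interval obtains a Youden variance about twice the one used for Table 1 (1.41² ≈ 2). The sample size of 30 would then appear to fall short of its 80% claim when, on the plan's own model, it does not.

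**Working it through.** **Inputs, all from section 8.2.** n = 30 per stratum and dose; ρ = 0.2; three samples per patient for each of sensitivity and specificity; design effect 1 + 2 × 0.2 = 1.4; sensitivity 0.75; specificity 0.70; Youden index 0.75 + 0.70 − 1 = 0.45; two-sided 95% multiplier 1.96.

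**1. The two intervals that reproduce.**

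- SE(sensitivity) = √(0.75 × 0.25 × 1.4 / 90) = 0.0540. Interval 0.75 ± 0.106 = (0.644, 0.856); printed (0.64, 0.86).
- SE(specificity) = √(0.70 × 0.30 × 1.4 / 90) = 0.0572. Interval 0.70 ± 0.112 = (0.588, 0.812); printed (0.59, 0.81).

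**2. The Youden interval.**

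- Adding limits: 0.64 + 0.59 − 1 = 0.23 and 0.86 + 0.81 − 1 = 0.67, as printed. Unrounded: half-width 0.106 + 0.112 = 0.218, giving (0.232, 0.668).
- Summing variances with zero covariance: SE = √(0.0540² + 0.0572²) = 0.0786. Half-width 1.96 × 0.0786 = 0.154, giving (0.296, 0.604).
- Ratio of half-widths: 0.218 / 0.154 = 1.41. Under the zero-covariance model the printed width covers about 99.4%.

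**3. Which covariance the plan used.** For a correct-selection probability of 80% at a Youden difference of 0.10, the required number per group is n = 0.8416² × V / 0.10², where V is n times the variance of the between-dose difference in Youden index. With zero covariance, V is the sum of the four p(1−p) terms multiplied by (1+2ρ)/3.

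Row 1 (0.75/0.70 against 0.60/0.75) has a p(1−p) sum of 0.1875 + 0.2100 + 0.2400 + 0.1875 = 0.825. Hence n = 0.7083 × 0.825 × 1.2 / 0.03 = 23.4 for ρ = 0.1, and 27.3 with 1.4 in place of 1.2 for ρ = 0.2.

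| | ρ = 0.1 | ρ = 0.2 |
|---|---|---|
| Row 1, printed | 23 | 27 |
| Row 1, zero covariance | 23.4 | 27.3 |
| Row 1, correlation +1 | 46.6 | 54.4 |
| Row 5, printed | 25 | 30 |
| Row 5, zero covariance | 25.4 | 29.6 |
| Row 5, correlation +1 | 50.7 | 59.1 |
| All rows, printed | 21–25 | 24–30 |
| All rows, correlation +1 | 41–51 | 48–59 |
| All rows, ρ also between tumor and normal samples | 16–19 | 14–17 |

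With zero covariance all 24 cells reproduce, the largest deviation being 0.81 patients. Neither alternative comes close.

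**4. Other constructions of the interval.** None of these gives (0.23, 0.67): the joint confidence level described in section 8.1 gives (0.274, 0.626); a 99% level (0.248, 0.653); a t distribution with 29 degrees of freedom (0.289, 0.611).

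**5. Effect on the design claim.** In row 5 at n = 30 and ρ = 0.2, the correct-selection probability is 0.802 with zero covariance. It would be 0.726 with the correlation of +1 that the printed interval implies.

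**The case against.** The strongest defence is that section 8.2 states no covariance. Under the normal model, added limits cover exactly 95% at correlation +1 and at least 95% at any other correlation, so they are a valid conservative bound. That is true, but the plan labels the figure simply as a 95% interval, says nothing of conservatism, and uses zero covariance for the table beside it.

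Three further points deserve weight.

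- **The mechanism is inferred.** A half-width inflated by √2, such as that for a difference between two doses with equal variances, is 1.96 × 0.0786 × √2 = 0.218 and prints the same limits. The document cannot separate the two origins. Under either one, the figure is not the 95% interval for a single dose's Youden index at n = 30.
- **Zero covariance is also inferred.** The definition of ρ could be read to cover tumor–normal pairs from one patient. A patient whose tissue tends to fluoresce throughout would then gain sensitivity and lose specificity, so the covariance is negative: −0.2 × √(0.1875 × 0.21) / 30 = −0.00132. The SE becomes 0.0595 and the interval (0.333, 0.567), further still from the printed one. Table 1 rules this reading out as the one used. The match to Table 1 is not perfect to the digit: 20 of the 24 cells agree by nearest rounding, and the four in rows 3 and 12 appear truncated (for example 24.65 printed as 24).
- **No decision uses the interval.** Dose choice rests on observed Youden indices, and the intervals planned in section 8.1 are for the true and false positive fractions. This stands, and it keeps the point minor.

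**Conclusion.** The printed Youden interval is wrong as a 95% interval under the plan's own working model. It should be (0.296, 0.604), or (0.30, 0.60) to two decimals. The printed half-width is 0.218 unrounded, against 0.154. This rests on the variances stated in section 8.2 and on zero covariance between the sensitivity and specificity estimates, which the text does not state but Table 1 requires.

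The error is minor and conservative, because it understates the planned precision. At n = 30 the correct-selection probability is between 0.80 and 0.84 across all rows of Table 1 and both values of ρ, so the sample size and the 80% claim stand.

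**What to change.** In section 8.2, replace (0.23, 0.67) with (0.30, 0.60) and add a clause saying that it assumes zero covariance between the sensitivity and specificity estimates, as Table 1 does. If the wider interval was intended, keep it but label it a conservative bound with coverage above 95%; the first option is better because it agrees with the table.

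If a Youden interval is reported at analysis, compute it from the patient-clustered variance of sensitivity plus specificity, not by adding limits. This follows the commitment in section 8.1 to allow for correlation between specimens from one patient.

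The cost is one figure and one clause. The sample size, Table 1 and the selection rule do not change.
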